3.2. Subject Enrollment and Treatment Allocation

Subjects will be recruited from multiple CF centers in the US. Forty male and female patients with CF, 18 years of age or older, are planned to participate in the study. This will be a 3-part study with 16 subjects participating in Part A; 16 subjects participating in Part B; and 8 subjects participating in Part D.

Subjects will not be allowed to participate in more than 1 part of the study.

At the initial screening visit, informed consent will be obtained from the subject. A unique subject identification number will then be assigned, which will serve as the subject's identifier throughout the study and in the case report form (CRF). Subjects in Parts A and B will be randomized to treatment and thereby enrolled in the study after the following 2 conditions have been met:

1. Subject meets all of the inclusion criteria and none of the exclusion criteria during the screening period and Day -1.
2. Confirmation of eligibility on Day 1. Results from the Day -1 and pre-dose tests on Day 1 (AE, conmeds, pulse oximetry, physical exam, vital signs) do not reveal a new safety issue making the subject ineligible for randomization. A subject is considered enrolled into the study when he or she has been randomized to treatment. Pre-dose tests that may occur after randomization but MUST occur and be reviewed by the PI prior to first dose include spirometry and ECG. If the pre-dose Day 1 ECG or spirometry results reveal a safety issue making it inadvisable to administer the dose to the randomized subject, then the subject will be considered an Early Discontinuation.

Subjects in Part D will be randomized to treatment and thereby enrolled in the study after the following 2 conditions have been met:

1. Subject meets all of the inclusion criteria and none of the exclusion criteria during the screening period.
2. Confirmation of eligibility on Day 1 prior to randomization. Results from the Day 1 pre-dose assessments (AE, conmeds, pulse oximetry, physical exam, vital signs, pregnancy test [female subjects only]) do not reveal a new safety issue making the subject ineligible for randomization. A subject is considered enrolled into the study when he or she has been randomized to treatment.

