3.2.3. Part D

Eight subjects will be randomized in a 3:1 ratio to receive 5 doses of either 4 mg MRT5005 or placebo, administered at 1 dose per day for 5 consecutive days. Based on the safety experience gained in Parts A and B, the enrollment and treatment of the 8 subjects in Part D will not be staggered. During the treatment of subjects in Part D, should AEs occur that indicate the study drug is not tolerated well, the enrollment and treatment of subjects may be terminated by the PSRC and Sponsor, and enrollment and treatment of a lower dose strength may be considered in the remaining subjects in the cohort. For example, if the tolerability of the 4 mg daily dose level is found to be unacceptable, then the 2 mg dose level can be considered for investigation.

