7.1.1.2. Rescreening of Subjects

Based on Investigator discretion and Sponsor approval, subjects who initially failed to meet the inclusion/exclusion criteria may be rescreened at a later time if their eligibility status has changed (eg, resolution of a transient event such as an acute upper respiratory infection or pulmonary exacerbation).

For subjects who initially met all inclusion/exclusion criteria, but due to scheduling conflicts or study delays were unable to enroll into the study within the screening period window, based on the Investigator's discretion and Sponsor's approval, the subject may be allowed to enroll by extending the window for the screening period or may choose to be rescreened at a later time.

Enrolled subjects who discontinue treatment after one dose of study drug for a reason unrelated to safety (eg, interrupted clinical research activities due to coronavirus disease pandemic) may be rescreened at a later time at the discretion of the Sponsor. Such subjects may receive no more than 5 weekly doses of study drug in total.

In all cases of rescreening, a new informed consent form must be signed by the subject.
Rescreened subjects who did not enroll in the study will retain the same subject identification number that he/she was assigned at the first screening. Rescreened subjects who previously enrolled in the study will be assigned a new subject identification number.

7.1.2. Treatment Period: Day -1 to Day 2

See [Table 1](#) for the Schedule of Procedures for the treatment period of Part A.

Following screening, eligible subjects will return to the study center on Day -1 of the treatment period. Subjects will be admitted to the study center on Day -1 and will be confined to the study center (inpatient) until discharged on Day 2.

On Day -1, the baseline procedures and tests as described in [Table 1](#) will be performed. The Day -1 results must be reviewed by the Investigator to ensure that subjects continue to be eligible for study enrollment (see Section [7.1.1.1](#) for definition of screening failure).

Pre-dose assessments on Day 1 include a limited physical examination, measurement of vital signs and oxygen saturation (pulse oximetry), and ECG and spirometry testing. The limited physical examination, vital signs and pulse oximetry must be performed prior to randomization. ECG and spirometry may be performed after randomization, but MUST be performed, and reviewed prior to the dose, to confirm continued eligibility.

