7.2.1.2. Rescreening of Subjects

Rescreening of subjects, as described in Section [7.1.1.2](#) for Part A, also applies to Part B.

7.2.2. Treatment Period: Day -1 to Day 33

See [Table 4](#) and [Table 7](#) for the Schedule of Procedures for the treatment period of Part B.

Following screening, eligible subjects will return to the study center on Day -1 and will perform the baseline procedures and tests, as described in Table 4. The Day -1 results must be reviewed by the Investigator to ensure that subjects continue to be eligible for study enrollment (see Section [7.1.1.1](#) for definition of screening failure).

Subjects will return to the study center the following day (Day 1). Pre-dose assessments on Day 1 should be performed immediately prior to IP administration; these assessments include a limited physical examination, measurement of vital signs and oxygen saturation (pulse oximetry), and spirometry testing. If the subject is receiving treatment with an inhaled short-acting bronchodilator as part of their routine pulmonary therapies (see below), pre-dose spirometry testing may be scheduled before the subject's pulmonary therapies (if the subject's schedule permits) so that it can be performed "pre-bronchodilator." Alternatively, the subject may choose to delay the bronchodilator treatment until after the pre-dose spirometry testing is performed and receive the treatment just prior to the administration of IP, as described below. Recording of any AEs and concomitant medications should continue at this time. The procedures and tests performed on Day -1 and pre-dose on Day 1 will be used to confirm eligibility; these results will only be exclusionary for subjects if there is a clinically significant or relevant change in a result, as determined by the Investigator (eg, positive pregnancy test).

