7.3.1.2. Rescreening of Subjects

Rescreening of subjects, as described in Section [7.1.1.2](#) for Part A, also applies to Part D.

7.3.2. Treatment Period: Day 1 to Day 5

See [Table 8](#) for the Schedule of Procedures for the treatment period of Part D.

Following screening, eligible subjects will return to the study center on Day 1 and will perform the baseline procedures and tests, as described in [Table 8](#).

Pre-dose assessments on Day 1 should be performed prior to IP administration; these assessments include a pregnancy test (female subjects only), collection of blood for safety labs, limited physical examination, measurement of vital signs and oxygen saturation (pulse oximetry), and spirometry testing. If the subject is receiving treatment with an inhaled short-acting bronchodilator as part of their routine pulmonary therapies (see below), pre-dose spirometry testing may be scheduled before the subject's pulmonary therapies (if the subject's schedule permits) so that it can be performed "pre-bronchodilator." Alternatively, the subject may choose to delay the bronchodilator treatment until after the pre-dose spirometry testing is performed and receive the treatment just prior to the administration of IP, as described below. Recording of any AEs and concomitant medications should continue at this time. The only procedures and tests performed pre-dose on Day 1 that will be used to confirm eligibility are the limited physical exam, vital signs, pregnancy test, and pulse oximetry; these results will only be exclusionary for subjects if there is a clinically significant or relevant change in a result, as determined by the Investigator (eg, positive pregnancy test).

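### Could a person who re-enters under a new subject number be counted twice in the safety tables?

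*Protocol*

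**What the plan says.** Protocol 7.1.1.2 (Rescreening of Subjects) opens a narrow route back into the study for "Enrolled subjects who discontinue treatment after one dose of study drug for a reason unrelated to safety", with interruption by the pandemic as its example. Exclusion criterion 15 makes the matching exception. Three conditions apply. The first is fresh consent: "In all cases of rescreening, a new informed consent form must be signed by the subject". The second is a new number: "Rescreened subjects who previously enrolled in the study will be assigned a new subject identification number". The third is a limit on exposure: "Such subjects may receive no more than 5 weekly doses of study drug in total". Protocol 7.2.1.2 and 7.3.1.2 carry the rule over by stating that what is described "for Part A, also applies to Part B" and "for Part A, also applies to Part D". Protocol 3.2 adds: "Subjects will not be allowed to participate in more than 1 part of the study".

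SAP 4.1 defines the safety set as everyone randomized and dosed, analyzed as treated. SAP 9.3.1 and 9.3.2 use the number of subjects in that set as the denominator. SAP 9.3.2 counts a subject once per system organ class and once per preferred term. The SAP text available does not mention rescreening or a second number.

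**The concern.** Protocol 7.2.1 makes the subject number the identifier in the CRF, and the SAP listings are sorted by it. A program keyed on that number would see two subjects, each randomized and dosed, so each would meet the safety set definition. Because a subject may join only one part, both records would fall in the same by-part tables.

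Two further effects are possible. Protocol 4.5.1 asks that dosed subjects who discontinue be followed for the rest of the study, while event collection under the second number starts at the new consent. One event could therefore be entered under both numbers. The second record's spirometry baseline could also follow a study dose. Safety is the primary endpoint and is purely descriptive, so distorted percentages in such small columns would be distorted primary results.

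**Working it through.** **Planned counts.** Protocol 3.2 gives 16 + 16 + 8 = 40, which agrees with 4×4 + 4×4 + 8. Each Part A and Part B group has 3 MRT5005 and 1 placebo; Part D at 3:1 has 6 and 2 (SAP 2.5). A Part B dose column is therefore 3 and Part B pooled placebo is 4. The all-parts totals are 12 + 12 + 6 = 30 MRT5005 and 4 + 4 + 2 = 10 placebo. Part A gives a single dose, so the question concerns Parts B and D.

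**If programs counted numbers.** Assume one re-entry, both records in the same column of p persons, and only the re-entered person has the event. The true rate is 1/p. It shows as 1/(p+1) if recorded under one number and 2/(p+1) if recorded under both.

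| Column | p | True | One number | Both numbers |
|---|---|---|---|---|
| Part B dose group | 3 | 33.3% | 25.0% | 50.0% |
| Part B pooled placebo | 4 | 25.0% | 20.0% | 40.0% |
| Part D 4 mg | 6 | 16.7% | 14.3% | 28.6% |
| Part D placebo | 2 | 50.0% | 33.3% | 66.7% |
| All parts, MRT5005 | 30 | 3.3% | 3.2% | 6.5% |
| All parts, placebo | 10 | 10.0% | 9.1% | 18.2% |

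For exposure in a Part B dose column, three people with 5 doses each have mean 5.0 (SD 0). Splitting one of them into 4 + 1 gives (5 + 5 + 4 + 1)/4 = 3.75 (SD 1.89).

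**Whether the second record takes another planned slot.** After one dose, at most 5 − 1 = 4 remain. SAP 2.3 sets 4 completed doses as the evaluable minimum in Parts B and D, so the one-dose record is not evaluable and the second can be. If the second number used up another planned place, Part B would end with 15 evaluable and Part D with 7, short of the 16 and 8 in Protocol 4.5.2 (replacement there is at the sponsor's discretion). The added-record case above is thus the natural one.

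**Whether both records share a column.** The documents do not say whether the first assignment is kept. If it is, the arm is the same. If the person is randomized again independently at 3:1 (an assumption), the same arm recurs with probability 0.75² + 0.25² = 0.625. A shared MRT5005 column in Part B also needs the same dose level.

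**What the text means by a subject.** Protocol 7.1.1.2 separates the subject from the number: the rescreened subject continues and is given another number. The cap "Such subjects may receive no more than 5 weekly doses of study drug in total" makes sense only for a person across both entries. The one-part rule likewise restrains people. On that reading SAP 9.3.2 already counts the person once, and the SAP 3 baseline, the last value before the first dose, is the value before the first study dose. The CRF numbering and the listing sort order are record-keeping; they do not define the unit of analysis.

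**Whether anyone is affected.** The one discontinuation after a first dose that the documents describe is a Part B 16 mg subject, listed in Protocol 2.2.3 among the febrile reactions. If that was the reason for stopping, the non-safety route is closed to that person.

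**The case for a change.** The best case for a change is that the protocol deliberately created this route, the SAP is silent on it, and the repair is cheap. The counted-once rules remove repeat events within a subject; they do not by themselves join two numbers. Treatment-emergent status and study day run from treatment start, so one event could be classed differently under each number. In columns of 2 to 6, a single duplicate moves a percentage visibly.

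The silence is real, and if someone re-entered, the study report should say so and show how the two records were joined. What does not stand is that the plan, as written, gives a wrong result. That requires reading a subject as a person when placing both records in one part, and as a number when counting them. The inflated figures also need one event entered twice; nothing says the first record stays open after re-consent.

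A duplicate would also be hard to miss. The Part B and Part D exposure tables print each subject's dose counts, so 5, 5, 4, 1 would stand beside the mean of 3.75. The disposition listing gives dosing dates and the withdrawal reason, and the demographics listing gives date of birth and mutations. This visibility aids detection; it would not itself correct a table.

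**Conclusion.** The concern is understandable but does not call for a change. The plan leaves a linking rule unwritten; it does not state a wrong one. Read consistently, a subject is a person, and the SAP's counting and baseline rules then give the right answer. If nobody re-entered, the effect is nil. If one person did, the table's distortions arise only if programs count by number and both records share a column. No hypothesis test depends on the result.

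This rests on the SAP text available and on the absence of any reported re-entry. Separately, the cap is worded in weekly doses and is applied to Part D, where dosing is "administered at 1 dose per day for 5 consecutive days". Those passages must be reconciled, but this is a matter of wording and does not affect how people are counted.

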7.2. Part B Study Schedule

Details regarding the procedures and tests to be performed during each study period and time point for Part B are provided in the Schedule of Procedures in [Table 4](#), [Table 5](#), [Table 6](#), and [Table 7](#).

Similar to Part A of this study, Part B will consist of a screening period, a treatment period, and a follow-up period (see [Figure 1](#)). The duration of the screening period is up to 27 days (Day -28 through Day -2); the duration of the treatment period is 36 days (Day -1 to Day 35); and the duration of the follow-up period is up to 332 days (Day 36 through Day 365 [± 3 days]). No confinement (inpatient) will be required of subjects in Part B; subjects will perform all clinic visits as outpatients.

All AEs and SAEs, regardless of relationship, will be collected from the time of informed consent signing until the final study visit on Day 365 (± 3 days). Information on all prior and concomitant medications administered from 30 days before the date of informed consent signing through the final study visit on Day 365 (± 3 days) must be recorded on the appropriate CRF page.

Time Windows for the Schedule of Procedures:

No obligatory time windows are set for the study time points in order to allow for flexibility in the conduct of the study. The time windows provided in [Table 4](#), [Table 5](#), [Table 6](#), and [Table 7](#) are suggested guidelines to be followed during the conduct of Part B. As these guidelines are only suggestions, they will not result in protocol deviations.

Priority Order for Performing Procedures and Tests:

The following priority order will be in effect when more than 1 procedure or test is required at a particular time point.

- AE, concomitant medication, and concomitant surgical procedure reporting
- Vital signs, pulse oximetry
- Physical examination
- Spirometry
- Clinical laboratory tests (serum chemistry, hematology, coagulation, urinalysis, CRP)
- ECG

- Chest x-ray
- Other procedures with lower priorities (weight measurement; blood sampling for [REDACTED] mRNA and [REDACTED] assays, and for immune response assays)

On the days when serum or urine pregnancy testing is being performed, scheduled or unscheduled, this test has priority.

7.2.1. Screening Period: Day -28 to Day -2

See [Table 4](#) for the Schedule of Procedures for the screening period of Part B.

Written, signed, and dated informed consent must be obtained by the Investigator or a designee from the subject prior to the performance of any study-related procedures or tests. A copy of the signed informed consent form must be given to the subject for their records.

At the initial screening visit, informed consent will be obtained from the subject. A unique subject identification number will then be assigned, which will serve as the subject's identifier throughout the study and in the CRF. Inclusion and exclusion criteria will be reviewed to assess the subject's eligibility; and demographic information, and medical and medication history will be collected. Collection of AEs and concomitant medications will begin from the time the subject signs the informed consent.

Subjects participating in Part B of the study will perform all of the same procedures and tests during the screening period as in Part A. All screening procedures and tests must be completed during the screening period and prior to returning to the study center on Day -1. Multiple visits during the screening period may be necessary for the subject to complete all of the required screening procedures and tests. If a screening test is considered to be invalid upon subsequent review (eg, spirometry testing) or not representative of the subject's usual baseline status, it may be repeated at the discretion of the Investigator. All screening procedures and tests are to be performed by the Investigator or a qualified designee.

The baseline chest x-ray may be performed at any time from Day -14 to Day -2 during the screening period. If feasible for the subject, all spirometry testing for the study should be performed "pre-bronchodilator" for those subjects receiving treatment with a short-acting beta-agonist or anticholinergic bronchodilator, as described in Section [7.5.2.12](#).

Subject eligibility for the study will be determined based on the procedures and tests performed during the screening period. As described in Section [7.1.2](#), subsequent testing performed on Day -1 and Day 1 will be used to confirm eligibility. A clinically significant or relevant change in a result during pre-dose assessments, as determined by the Investigator, may be exclusionary (eg, new or worsening adverse event or worsened pulse oximetry reading).

7.2.1.1. Screening Failure

The definition of a subject who is a screen failure, as described in Section [7.1.1.1](#) for Part A, also applies to Part B.

7.2.1.2. Rescreening of Subjects

Rescreening of subjects, as described in Section [7.1.1.2](#) for Part A, also applies to Part B.

7.2.2. Treatment Period: Day -1 to Day 33

See [Table 4](#) and [Table 7](#) for the Schedule of Procedures for the treatment period of Part B.

Following screening, eligible subjects will return to the study center on Day -1 and will perform the baseline procedures and tests, as described in Table 4. The Day -1 results must be reviewed by the Investigator to ensure that subjects continue to be eligible for study enrollment (see Section [7.1.1.1](#) for definition of screening failure).

Subjects will return to the study center the following day (Day 1). Pre-dose assessments on Day 1 should be performed immediately prior to IP administration; these assessments include a limited physical examination, measurement of vital signs and oxygen saturation (pulse oximetry), and spirometry testing. If the subject is receiving treatment with an inhaled short-acting bronchodilator as part of their routine pulmonary therapies (see below), pre-dose spirometry testing may be scheduled before the subject's pulmonary therapies (if the subject's schedule permits) so that it can be performed "pre-bronchodilator." Alternatively, the subject may choose to delay the bronchodilator treatment until after the pre-dose spirometry testing is performed and receive the treatment just prior to the administration of IP, as described below. Recording of any AEs and concomitant medications should continue at this time. The procedures and tests performed on Day -1 and pre-dose on Day 1 will be used to confirm eligibility; these results will only be exclusionary for subjects if there is a clinically significant or relevant change in a result, as determined by the Investigator (eg, positive pregnancy test).

Prior to IP administration, subjects should undergo their routine pulmonary therapies (airway clearance and pulmonary medications). These may be administered either at home or at the study center and may include but are not limited to chest physiotherapy, and treatment with inhaled bronchodilators, hypertonic saline, antibiotics, and steroids (Section [5.1.1](#)). The administration of IP should optimally occur within 2 to 3 hours after subjects have completed their pulmonary therapies for the day. For subjects whose routine pulmonary medications do not include an inhaled short-acting beta-agonist (or it is not given within the 2 to 3 hour window prior to IP administration), albuterol (2 to 4 puffs) will be administered via metered-dose inhaler approximately 20 minutes before treatment with IP to minimize any potential bronchoconstrictive effects (Section [5.1.1.1](#)). Note that administration of a short-acting beta-agonist via nebulization is also permitted at the discretion of the Investigator

Following confirmation of eligibility, subjects will be randomized to receive the first dose of either MRT5005 or placebo (subjects who are randomized are considered enrolled into the study). The administration of IP will be performed by a blinded, qualified member of the study staff. IP will be administered by the respiratory route using an InnoSpire Go nebulizer. Depending on the dose level, nebulization times will range from approximately 44 to 133 minutes. During nebulization, blood pressure, pulse rate, and oxygen saturation measured by pulse oximetry will be monitored continuously, together with close monitoring of the subject for any signs or symptoms of respiratory distress (eg, dyspnea, wheezing, bronchospasm). See

Section [6.2.2](#) for details on the preparation and dosing of IP, which includes minimizing secondary exposure to study staff during nebulization of IP.

The second through fifth doses of IP will be administered on Days 8, 15, 22, and 29, respectively. IP dosing should occur on approximately the same day of Weeks 1 through 5 (eg, every Tuesday [the day of the week is defined by the first dose given on Day 1 of Week 1]), but may occur ± 1 day of the target day for Weeks 2 through 5 in order to facilitate subject scheduling. The pre-dose assessments will be identical to those performed for the first dose (with some additional pre-dose assessments on Days 8, 15, 22, and 29 as noted in [Table 7](#)), and IP should continue to be administered within 2 to 3 hours after subjects have completed their routine pulmonary therapies. In addition, instructions regarding the use of rhDNase (PULMOZYME) and short-acting beta-agonist therapies should continue to be followed for all doses.

On dosing days ([Table 7](#)), subjects will remain in the clinic for safety monitoring for at least 6 hours after administration of IP and will be discharged only when deemed clinically stable by the Investigator with no ongoing AEs or safety concerns of clinical significance. Discharged subjects can go home if they live locally (within 1 hour driving distance from the study center) or if not should be housed overnight close to the study center until the clinic visit on the following day. If a subject is experiencing an ongoing AE or there is a safety concern at the 6-hour time point (eg, decreased oxygen saturation by pulse oximetry or airway symptoms), based on the judgment of the Investigator, the subject can remain in the study center overnight or can be hospitalized for continued monitoring until the clinic visit on the following day. The subject should remain in the study center or hospital until the AE or safety concern has resolved and the subject is sufficiently stable to be discharged.

Subjects will be provided a digital thermometer and Body Temperature Recording Log for measuring and recording his/her body temperature after discharge on each dosing day. Subjects will be asked to record his/her body temperature at regular intervals until bedtime and as needed overnight should febrile symptoms (eg, chills, night sweats) awaken the subject from sleep on each dosing day.

At discharge on each dosing day, subjects will be instructed to return to the clinic on the following day (Days 2, 9, 16, 23, and 30). The procedures and tests, as described in Table 4, will be performed at this post-treatment clinic visit. Following these outpatient clinic visits, subjects will be contacted approximately 3 days later by telephone on Days 5, 12, 19, 26, and 33, to query the subject about the occurrence of any AEs/SAEs and any changes in concomitant medications.

If a subject is experiencing respiratory distress or respiratory symptoms, based on the Investigator's judgment, unscheduled spirometry testing may be performed when the subject is stable. In addition, at the discretion of the Investigator, an unscheduled chest x-ray may be performed at any time during the treatment period if the subject is experiencing respiratory symptoms that warrant it.

During the clinic visits and telephone contacts, subjects will be reminded to return to the study center or call the study staff immediately, if they are experiencing any symptoms of concern,

either new or worsening, or were hospitalized or required a visit to the emergency department for any reason.

7.2.3. Follow-up Period: Day 36 to Day 365

See [Table 5](#) and [Table 6](#) for the schedule of procedures for the follow-up period of Part B.

Safety will be monitored for 12 months after administration of the fifth dose of IP in Part B. The safety follow-up period continues through the last study visit on Day 365 (± 3 days).

Subjects will return for outpatient clinic visits on Days 36, 43, 57, 71, 85, 113, 197, 281, and 365 to perform the follow-up procedures and tests scheduled for this period. Telephone contact with the subject will occur on Days 39, 46, 50, 64, 78, 99, 141, 169, 225, 253, 309, and 337 to query the subject about the occurrence of any AEs/SAEs and any changes in concomitant medications. Subjects will also be instructed at every clinic visit and telephone contact to return to the study or call the study staff immediately if they are experiencing any symptoms of concern, either new or worsening, or were hospitalized or required a visit to the emergency department for any reason.

If a subject is experiencing respiratory distress or respiratory symptoms, based on the Investigator's judgment, unscheduled spirometry testing may be performed when the subject is stable. In addition, at the discretion of the Investigator, an unscheduled chest x-ray may be performed at any time during the follow-up period if the subject is experiencing respiratory symptoms that warrant it.

Study completion for each subject is defined as the last study assessment for that subject on Day 365 (± 3 days). All ongoing AEs on Day 365 must be followed to closure (when the subject's health has returned to his/her baseline status or when all variables have returned to normal). Closure indicates that an outcome is reached, stabilization achieved (the Investigator does not expect any further improvement or worsening of the event), or the event is otherwise explained. When appropriate, medical tests and examinations may be performed so that resolution of event(s) can be documented.

